6.11 Concomitant Medication Assessments

A concomitant medication is any medication that the subject has been taking prior to enrollment and that the subject is expected to continue to take for some portion of the trial, as well as any medication other than the investigational product that the subject takes during the course of the trial.

The medications or treatment for controlling hypoglycemia must be recorded as concomitant medications in the CRF. Any medication given to treat hyperglycemia is considered a rescue therapy and should be recorded in the concomitant medication log.

Changes from baseline anti-hypertensive therapy and their rationale must be recorded in the CRF.

All prescription and over-the-counter medications, including vitamins and herbal supplements, that subjects receive during the trial must be documented on the CRF. This documentation should continue until the subjects complete the study.

Concomitant medications will be coded using the World Health Organization Drug Dictionary (WHO-DD). A table of concomitant medications based on the anatomic

therapeutic chemical classification (ATC) and preferred name will be produced. A listing of concomitant medications will include all medications taken by any subjects during the course of the study.

6.12 Removal of Patients from the Trial or Discontinuation of Investigational Product Administration

The investigator must emphasize to potential subjects the importance of continued participation for the full duration of the trial during the informed consent process. Potential subjects should be informed that the trial procedures will allow additional medications to control hyperglycemia or other adverse conditions. It is also important to emphasize that missing data and missed visits could affect the entire trial. If subjects are dissatisfied with the conduct of the trial but have not withdrawn, the investigator should make an effort to address their concerns and retain them in the trial if possible. In doing so, investigators must be careful that the efforts do not cross over into coercion. Investigator should encourage a subject to remain in the study even if the investigational product administration is stopped so that safety information can be collected.

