2.2 STUDY DESIGN

A brief summary of the main study design features and assessments to be performed is presented here. Refer to Section 3 of the study protocol for complete details.

This is a Phase 2b, multi-center, double-blind, placebo-controlled parallel group, dose range finding study of once daily bexagliflozin tablets in either treatment-naïve type 2 diabetes subjects or subjects previously treated with one OHA. Treatment-naïve subjects are those who have never received prescription anti-diabetic medications or who have received no more than 14 days of prescription medications for diabetes in the 12 weeks prior to enrollment. Subjects who meet all of the inclusion criteria, none of the exclusion criteria and who consent to participate in the study are eligible to be enrolled to complete a 6 to 10 week washout (only required if the subject is not treatment naïve), and a 2 week placebo run-in period prior to being randomized. Subjects who can adhere to the run-in medication dosing scheduled (i.e., miss no more than one dosage in 2 weeks) and who have HbA1c between 7 and 8.5% at baseline will be eligible for randomization. Eligible subjects will be randomized to receive oral bexagliflozin tablets, 5, 10, 20 mg or placebo, once daily for 12 weeks in an outpatient setting. Subjects will visit their study site at weeks 2, 6 and 12 for safety and efficacy evaluation, with a follow up visit at week 14.

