3.2 Analysis Populations and Subgroups

3.2.1 Definition of Analysis Populations

All Enrolled

All subjects who signed an informed consent form will be included in the all enrolled analysis set.

Full Analysis Set

All subjects who are randomized, take at least one dose of double-blind study medication, and have at least one post-randomization HbA1c measurement will be included in the full analysis set. All analyses of the full analysis set will be based on each subject's randomized assigned treatment.

Intent-to-Treat Analysis Set

All subjects who are randomized will be included in the intent-to-treat analysis set. All analyses of the intent-to-treat analysis set will be based on each subject's randomized assigned treatment.

Safety Analysis Set

All subjects who are randomized and take at least one dose of double-blind study medication will be included in the safety analysis set. Safety analyses will be based on the medication that was actually dispensed to each subject.

Per Protocol Analysis Set

The per protocol (PP) analysis set will include all subjects in the full analysis set who meet the study eligibility requirements as defined in Section 4 of the study protocol and have no major protocol deviations that affect the validity of the efficacy measurements. All analyses of the per protocol analysis set will be based on each subject's randomized assigned treatment. Major protocol deviations are defined as:

- Study drug compliance <80%
- Missing baseline or Week 12 HbA1c measurement
- Received prohibited medication including SGLT2 inhibitor, insulin or GLP-1 receptor agonists
- Randomization error
- Inappropriate unblinding (i.e., blind was broken (requested in IWRS) in absence of medical emergency or blind broken by unauthorized site personnel)
- Subject was dispensed with incorrect study medication

Subject exclusions will be determined on a case-by-case basis during a blinded review of the data prior to database lock. In addition, a blinded review of concomitant medications will be performed to further identify any other potential restricted medications.

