3.3.4 Other Variables

- Incidence of discontinuations and reasons for discontinuations from the study and, separately, from treatment
- Incidence of concomitant medications used

- Number of weeks on study drug
- Percentage of study drug taken relative to the planned dose

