3.7 Treatment Compliance and Exposure

3.7.1 Compliance with Study Treatment

Compliance rates during the treatment period will be derived with the following formula:

$$100 * ((\text{Total number of tablets dispensed} - \text{Total number of tablets returned}) / (\text{Expected number of tablets to be taken over a subject's extent of exposure in days}))$$

Expected number of tablets to be taken over a subject's extent of exposure is based on the date of first study medication dose and the date of last study medication dose [i.e., $(\text{date of last study medication dose} - \text{date of first study medication dose}) + 1$]. If a subject is lost to follow-up, and therefore does not have a date of last study medication dose, the last visit date will be used as the date of last study dose to determine the expected number of tablets to be taken and it will be assumed that the subject did not take any tablets since the last visit date.

Compliance rates will be presented for the safety analysis set using summary statistics and percentage for the frequency distributions (0- $< 20\%$, 20- $< 40\%$, 40- $< 60\%$, 60- $< 80\%$, 80- $< 100\%$, 100- $\leq 120\%$) by treatment group and overall.

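### Compliance is measured only over each subject's own time on drug, so the 80% per-protocol criterion cannot detect early stopping and does not match the plain reading of the listed compliance variable

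*SAP*

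**What the plan says.** SAP 3.7.1 defines compliance as tablets dispensed minus tablets returned, divided by the tablets expected over the subject's exposure. The expected number "is based on the date of first study medication dose and the date of last study medication dose", counted inclusively. For a subject lost to follow-up without a last-dose date, "the last visit date will be used as the date of last study dose".

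Three other parts of the SAP bear on this measure:

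- SAP 3.3.4 lists "Percentage of study drug taken relative to the planned dose" and, as a separate variable, "Number of weeks on study drug".
- SAP 3.2.1 makes "Study drug compliance <80"% a major deviation for the per-protocol set and gives no other definition of compliance. The same list contains "Missing baseline or Week 12 HbA1c measurement". It contains neither a minimum treatment duration nor discontinuation of treatment. Exclusions are decided individually at a blinded review before database lock.
- SAP 2.2 gives the regimen: "once daily for 12 weeks in an outpatient setting".

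Protocol 6.12 asks the investigator to "encourage a subject to remain in the study even if the investigational product administration is stopped". Protocol 7.4.1 places the exit visit of an early terminator two weeks after the last dose. SAP 3.1.9 moves an early termination visit that falls outside every analysis window to the next scheduled time point.

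**The concern.** A per-protocol set is meant to hold subjects who received the treatment largely as planned. The only adherence criterion here is a ratio whose denominator shrinks when treatment stops. It catches missed tablets during exposure but not the plainest departure from the regimen, which is ending it early.

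Subjects who stopped long before Week 12 could then contribute off-drug HbA1c values to the analysis meant to show the effect in adherent subjects. The reported compliance rate would also answer a different question from the one SAP 3.3.4 appears to pose.

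**Working it through.** The plan gives no worked compliance figure, so there is nothing to reproduce. The check applies the SAP formula and compares it with the planned regimen.

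**Inputs.** One tablet daily for 12 weeks (SAP 2.2) gives 12 × 7 = 84 planned tablets. One bottle of 90 is dispensed at V1 (Protocol 5.9.2 and 6.8). The threshold is 80% (SAP 3.2.1). The Week 6 window is Days 36–50 and the Week 12 window Days 78–92 (SAP 3.1.9, Table 2). The exit visit is taken as exactly 14 days after the last dose.

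**Step 1: score of a subject who takes every tablet and then stops.** The SAP formula is 100 × (dispensed − returned) / (last dose day − first dose day + 1). The comparison is 100 × taken / 84.

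| Last dose | SAP 3.7.1 | Against 84 planned |
|---|---|---|
| Day 14 | 14/14 = 100% | 16.7% |
| Day 28 | 28/28 = 100% | 33.3% |
| Day 37 | 37/37 = 100% | 44.0% |
| Day 42 | 42/42 = 100% | 50.0% |
| Day 56 | 56/56 = 100% | 66.7% |
| Day 67 | 67/67 = 100% | 79.8% |
| Day 68 | 68/68 = 100% | 81.0% |

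Since 0.80 × 84 = 67.2, a planned-dose denominator flags every stop on or before Day 67. The SAP formula flags none of them.

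**Step 2: whether the Week 12 HbA1c requirement closes the gap.** It does so only in part.

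- A subject who stops drug but stays in the study, as Protocol 6.12 encourages, can give a true Week 12 sample whatever the stopping day.
- For a subject who terminates, a last dose on Days 37–63 puts the exit visit on Days 51–77. That is outside every window, so it maps to Week 12. A last dose on Days 64–67 puts it on Days 78–81, inside the Week 12 window. Stops on Days 37–67 (44.0% to 79.8% of plan) can therefore meet both criteria.
- For a subject who terminates with a last dose on or before Day 36, the exit visit is on or before Day 50 and maps to Week 2 or Week 6. Without a Week 12 value the subject is excluded.

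**Step 3: unreturned tablets.** The numerator treats a tablet not returned as taken. If the whole bottle stays out, a completer scores 90/84 = 107% and a Day 42 stopper 90/42 = 214%. Both pass, and the second lies above the top reporting band of 120%.

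**Step 4: size.** The planning effect is 0.5 points (Protocol 9.2). Let p be the share of an active arm retained in this way and f the share of the effect lost by Week 12. Neither is in the documents, so both are assumed. Dilution = p × f × 0.5.

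- Low: 0.02 × 0.50 × 0.5 = 0.005.
- Middle: 0.05 × 0.70 × 0.5 = 0.0175, about 0.02.
- High: 0.10 × 1.00 × 0.5 = 0.05.

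For scale, the standard error of a two-arm difference with SD 0.9 is 0.9 × √(2/70) = 0.152 with 70 per arm and 0.9 × √(2/80) = 0.142 with 80. The middle case is about one-eighth of a standard error, and the high case about one-third.

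**The case against.** The strongest reply is that SAP 3.7.1 is a deliberate choice. It measures adherence while on treatment and leaves persistence to other displays. SAP 3.4.1 tabulates treatment non-completion with reasons, SAP 3.7.2 summarises duration, and Table 14.1.4 shows duration and compliance together. This stands for description: a reader might infer that the compliance table hides early stopping, but the same table shows it. It does not stand for the per-protocol criterion, which uses the ratio alone.

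A reader might also infer that SAP 3.3.4 and 3.7.1 flatly contradict each other. The SAP does not define the planned dose, and it could mean one tablet a day over the exposure period. The plain reading is the 12-week regimen, particularly as weeks on drug is listed separately, but the supportable statement is a mismatch to be reconciled.

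Nor do the documents support the inference that every early stopper enters the per-protocol set. Those without a Week 12 HbA1c are excluded, and the blinded review may remove others. No written criterion directs it to do so.

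Unreturned bottles are a weaker point than they look. A score of 214% would stand out, and Protocol 5.8, 5.11 and 7.3.4 provide for recording consumption at visits and counting tablets at Week 12.

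Finally, a planned-dose denominator has its own cost. It makes membership of the set depend more on events after randomisation, including discontinuation for adverse events. That is a fair objection and has to be carried into the fix.

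**Conclusion.** The point holds for the per-protocol classification. As written, the 80% criterion cannot detect early stopping, and the measure behind it does not match the plain reading of SAP 3.3.4. The subjects concerned stopped on or before Day 67, have a Week 12 HbA1c from continued follow-up or from a mapped exit visit, and are not removed at blinded review. How many there will be cannot be known from the documents.

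The consequence is limited. The per-protocol set supports a sensitivity analysis of the primary endpoint (SAP 3.8.1), and the expected distortion is a dilution of roughly 0.005 to 0.05 HbA1c points on the assumed inputs.

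A reader might infer that the primary result is at risk. It is not, because the full analysis set does not use compliance. Per-protocol counts do enter the centre-pooling rule in SAP 3.1.8, but that rule is triggered by any centre with fewer than 5 subjects per arm. With about 320 subjects over at least the 20 centres named for PK sampling, the average is at most 320/20/4 = 4 per arm, so the trigger is met either way.

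It is worth correcting because the written rule misclassifies subjects and the correction is cheap.

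**What to change.** Make these changes before database lock and unblinding:

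1. For the per-protocol criterion in SAP 3.2.1 and the variable in SAP 3.3.4, define compliance as tablets taken divided by the planned 84. A fixed 84 does not penalise a completer seen early. With the Week 12 visit at Day 82 (Day 85 − 3) and the last dose the day before, the score is 81/84 = 96.4%.
2. Keep the SAP 3.7.1 ratio as the on-treatment descriptive measure beside treatment duration, labelled as such.
3. Where tablets are not returned, do not count them as taken by default. Use the consumption recorded in the CRF at each visit.
4. List the early stoppers excluded from the per-protocol set by arm and reason.

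The cost is SAP wording and one derived variable. The downside is a slightly smaller per-protocol set whose membership depends more on discontinuation after randomisation, including for adverse events. Item 4 lets readers judge whether that selection differs between arms.

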3.7.2 Exposure to Study Treatment

Treatment duration (weeks on treatment) will be described in the safety analysis set using summary statistics. Treatment duration will be calculated as follows: $[(\text{date of last study medication dose} - \text{date of first study medication dose}) + 1 \text{ day}] / 7$.

Summaries will also include the number and percentage of subjects who were exposed for at least 2, $> 2 - \leq 6$, $> 6 - \leq 12$, and $> 12 - \leq 13$ weeks.

If the last dose date is unknown, the date of the last visit will be used.

3.8 Efficacy Analysis

Unless otherwise specified, all efficacy analyses will be performed using the full analysis set.

3.8.1 Primary Efficacy Endpoint(s)

The primary endpoint is HbA1c change from baseline through 12 weeks, and the primary analysis is based on the available data and data obtained after rescue will be excluded and considered missing. Mixed model repeated measures (MMRM) analysis of covariance model (ANCOVA) with baseline HbA1c as a covariate will be fit to the available data, incorporating all visits at which HbA1c was measured for each subject including scheduled visits at Weeks 2, 6, and 12 as well as unscheduled visits for measurements of HbA1c. Treatment (placebo, 5 mg, 10 mg, 20 mg), study center, prior anti-diabetic treatment status, study visit and treatment-by-visit interaction will be applied as fixed effects and subject as a random effect.

A normal distribution will be assumed for the built-in probability distribution. Model assumption will be checked. An unstructured (UN) within-subject covariance structure will also be assumed. The Kenward-Roger approximation will be used to estimate the denominator degrees of freedom.

Sample SAS code for this analysis is as follows:

```
proc mixed data=temp method=reml covtest;  
  class subject visit treat prior center;  
  model change = visit treat prior center baseline visit*treat /  
  solution ddfm=KENWARDROGER;  
  repeated visit / subject=subject type=un;  
  lsmeans visit*treat / diff=all cl alpha=0.05;  
run;
```

In the case that this covariance matrix is not an appropriate estimate, other covariance structures (e.g., compound symmetry) will be considered and ultimately determined through graphical tools (i.e., plot of changes in covariance and correlation among residuals on the same subject over lag between times of observation) and information criteria [e.g., Akaike's Information Criteria (AIC)].

Descriptive statistics will be presented for the observed measurements as well as for change from baseline by treatment group and visit overall (all subjects) and by country.

Least squares (LS) means and the corresponding standard errors (SE) of the change from baseline over time will be presented by treatment. In addition, the time profile of these LS mean and SE values will be presented graphically.

Least squares means and the corresponding standard errors for the difference in the changes from baseline over time between each bexagliflozin dose group and placebo will also be presented. Two-sided 95% CIs for the difference in these changes between each active dose and placebo will be generated. P-values from the model effects and key comparisons (i.e., treatment difference at Week 12) will be presented.

- Sensitivity Analyses

The same MMRM model and methods as outlined above for the primary analysis will be repeated using the per protocol analysis set.

Missing Data

The MMRM model is one approach to obtain treatment effect estimates in the presence of missing data. As sensitivity analyses for missing data, the following sensitivity analyses will be performed on the primary efficacy variable for the full analysis set:

- 1) HbA1c values collected after start of rescue medication will be considered missing. Missing HbA1c data (for Weeks 2, 6, or 12) will be imputed through multiple imputation (MI) linear regression methods which assumes a monotone missing data pattern. If the missing data pattern does not follow a monotone missing data then the Markov Chain Monte Carlo (MCMC) method will be used. The covariates to be included in the imputation linear regression model are treatment, center, age, gender, race, BMI, prior anti-diabetic treatment status as well as previous visit HbA1c values. A total of 10 imputed datasets will be generated and then analyzed using the MMRM methods as outlined above for the primary analysis. The point and variance estimates from each of these 10 analyses will be calculated. These analyses results will be combined across the 10 datasets using the standard techniques for multiple imputed data sets through SAS PROC MIANALYZE in order to yield overall treatment comparison results on imputed data.
- 2) Missing HbA1c data will be imputed through last observation carried forward (LOCF), where a subject's prior post-baseline non-missing observation will be imputed for any missing post-baseline visit for which there is a prior non-missing value, and then analyzed using the MMRM methods as outlined above for the primary analysis. HbA1c values collected after the start of rescue medication will be considered missing.
- 3) HbA1c values collected after the start of rescue medication will NOT be considered missing, and the MMRM methods as outlined above for the primary analysis will be re-performed.

Dropout patterns may be assessed by graphical methods (e.g., Kaplan-Meier plot for time to drop-out).

- Tests for Interaction

For the primary efficacy model, specifically the MMRM ANCOVA model, a test for a significant treatment-by-baseline interaction will be performed in a separate model. If the treatment-by-baseline interaction is significant at an $\alpha=0.100$, then an analysis of variance (ANOVA) model will be used instead, removing the baseline covariate.

A treatment-by-study center interaction term will be added to the MMRM ANCOVA (or ANOVA) model used for the analyses of the primary efficacy variable. If a statistically significant treatment-by-study center interaction effect is observed at a 0.100 level, then separate analyses may be performed for each study center.

A treatment-by-country interaction term will be added to the MMRM ANCOVA (or ANOVA) model used for the analyses of the primary efficacy variable. A statistically significant treatment-by-country interaction effect will be declared at the 0.100 level. Separate analyses will be performed for each country.

Note that significant interactions, if only quantitative (and not qualitative) in nature, will not necessarily preclude data being pooled across the baseline covariate or across study centers for the primary analysis.

- Dose Response

A dose response analysis on the change from baseline in HbA1c to Week 12 for the full analysis set will be conducted. Mean change from baseline in HbA1c to Week 12 (on vertical axis) will be presented graphically by dose group (on horizontal axis). Assessments of linear and quadratic dose-response trends across dose groups will be constructed using the MMRM ANCOVA model used for the primary efficacy analysis with appropriate orthogonal polynomial contrasts. P-values for each orthogonal polynomial contrast will be presented. To account for the unequal spacing of the dose levels (0, 5, 10 and 20), the coefficients to be used for the contrasts are as follows:

Linear:	-0.591608	-0.253546	0.0845154	0.7606388
Quadratic:	0.5640761	-0.322329	-0.644658	0.4029115

The coefficients are derived based on the statistical method from Robson, D.S. 1959: A simple method for constructing orthogonal polynomials when the independent variable is unequally spaced. *Biometrics* 15(2): 187-191.

Additional models may be considered if the dose response curve appears to be highly influenced by any single dose group.

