5.4 Method of Assigning Patients to Treatment Groups

Eligible subjects who complete the run-in period and meet all study inclusion/exclusion requirements will be randomized in a 1:1:1:1 ratio to receive investigational product according to a computer-generated randomization schedule. Subjects will be assigned to treatment groups in sequential order as they qualify for the study, using a centrally located and managed IWRS. Randomization will be stratified according to background anti-diabetic treatment status (treatment naïve or taking one OHA).

The study will be conducted at multiple investigative sites and will likely involve variable numbers of subjects at each site. Enrollment will be on a competitive basis but each site will be capped at 32 subjects. Activation of investigational sites will be centrally controlled by IWRS. Subject randomization will be deactivated for all sites when the planned number of subjects is met. However, if a potential subject is in the washout period and wishes to participate in the study, the subject will be allowed to continue and, if eligible, to be randomized.

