9.2 Determination of Sample Size

Approximately 320 subjects will be randomized and equally allocated to receive bexagliflozin tablets, 5 mg, 10 mg, 20 mg, or placebo.

The sample size calculation for this study is based on a two group t-test with a two-sided significance at the 5% level and the following assumptions:

- 1) The placebo-corrected population mean change from baseline to Week 12 in HbA1c in the highest dose group of 20 mg will be -0.5%.
- 2) The pooled standard deviation for the change from baseline to Week 12 in HbA1c for the active and placebo groups will be 0.9%.

Under the above assumptions, an estimated sample size of 70 evaluable subjects per treatment arm yields approximately 90% power to detect a treatment difference between bexagliflozin and placebo. A sample size of 80 per arm has been selected to account for a potential drop-out and to allow adequate safety evaluation. The total sample size for this study will be 320 subjects.

This study will be conducted at multiple investigative sites and will likely involve variable numbers of subjects at each site. Enrollment will be on a competitive basis but will be capped at 32 subjects from each site.

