9.5 Analysis of Efficacy

All efficacy analyses will be performed based on the FAS. The primary endpoint analysis will also be conducted using the PP Analysis Set.

For the primary endpoint of HbA1c change from baseline over 12 weeks of treatment, the MMRM analysis of covariance model (ANCOVA) with baseline HbA1c as a covariate will be fitted to the available data, incorporating all visits at which HbA1c was measured for each subject including the scheduled visits at weeks 2, 6, and 12 as well as the unscheduled visits for measurement of HbA1c (National Research Council, 2010). Treatment, study center, and stratification factor for randomization (treatment naïve versus taking one OHA at baseline) will be applied as fixed effects, as will study week and study week-by-treatment interaction. From this model, an estimate of the treatment difference at week 12 will be generated, as will an assessment of whether this estimate is significantly different when comparing placebo with each dose of bexagliflozin at a two-sided 0.05 level of significance. An unstructured within-patient covariance structure will be assumed. HbA1c values obtained after the start of rescue medication will be excluded from this primary analysis.

The MMRM model is one approach to obtain treatment effect estimates in the presence of missing data. As sensitivity analyses for missing data, the following will be performed:

- 3) Missing HbA1c data (for weeks 2, 6, or 12) will be imputed via multiple imputation (MI), following which the MMRM will be repeated on the complete datasets with results combined across complete datasets using standard MI techniques; HbA1c values collected after the start of rescue medication will be considered missing.
- 4) Missing HbA1c data will be imputed via LOCF, following which the MMRM will be repeated; HbA1c values collected after the start of rescue medication will be considered missing.
- 5) HbA1c values collected after the start of rescue medication will NOT be considered missing, and the MMRM analyses will be re-performed.

For the primary efficacy model, a test for a significant baseline-by-treatment interaction will be performed in a separate model, using a 0.100 alpha level. If the baseline-by-treatment interaction is significant, then the ANCOVA assumptions are violated and an analysis of variance (ANOVA) model will be used instead, omitting the baseline covariate.

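### The primary MMRM imposes one baseline-HbA1c slope on every visit; adding baseline-by-visit is a cheap way to gain a little Week 12 precision if that slope grows over time

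*SAP*

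**What the plan says.** SAP 3.8.1 fits a mixed model for repeated measures to HbA1c change, with an unstructured within-subject covariance. The sample code reads "model change = visit treat prior center baseline visit*treat". Baseline is a main effect, and the only visit interaction is with treatment.

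Protocol 9.5 and the synopsis agree: baseline HbA1c is a covariate, and treatment, center and the stratification factor are fixed effects, "as will study week and study week-by-treatment interaction". The key comparison is the treatment difference at Week 12.

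The only baseline interaction in either document is treatment-by-baseline, tested in a separate model (SAP 3.8.1, Tests for Interaction). That test does not let the slope differ by visit. The SAP says that model assumptions will be checked but names no check of this one.

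**The concern.** Protocol 3.3 and 6.13 describe HbA1c as reflecting two to three months of glycemia. A Week 2 change can therefore show only part of what Week 12 shows, and the same may hold for its dependence on baseline. When slopes differ by visit, a single coefficient is a weighted compromise, and an unstructured covariance gives most weight to the visit with the smallest variance. That is Week 2, whereas the key comparison is at Week 12. At stake is how much of the intended baseline adjustment reaches that comparison, and so its standard error.

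**Working it through.** **1. The plan's own figure.** Protocol 9.2 is "based on a two group t-test with a two-sided significance at the 5% level", with a difference of 0.5 and an SD of change of 0.9.

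- Normal approximation: 2 x (1.960 + 1.282)^2 x 0.81 / 0.25 = 68.1, so 69 per arm.
- Exact noncentral t: 70 is the smallest n reaching 90%. Power is 90.4% at 70 and 93.7% at 80 per arm.

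This agrees with "an estimated sample size of 70 evaluable subjects per treatment arm yields approximately 90% power". The 0.9 is the SD of change itself, so no credit is taken for baseline adjustment.

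**2. Inputs.**

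- From the documents: Week 12 SD 0.9; 70 evaluable per arm, so 280 in four arms; baseline HbA1c limited to 7.0-8.5% (Protocol 4.2).
- Assumed: SD of change 0.35 at Week 2 and 0.65 at Week 6.
- Assumed: baseline SD 0.30 to 0.433. The upper value is a uniform spread over the window, 1.5/sqrt(12).
- Assumed: residual correlations for Weeks 2-6, 2-12 and 6-12 of 0.5/0.3/0.6 (lower set) or 0.7/0.5/0.8 (higher set).
- Assumed: the slopes in the table below.

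**3. Formulas.** Let V be the baseline variance, B the vector of visit slopes, b12 its Week 12 element, and R the residual covariance about the visit-specific lines. The Week 12 residual variance is r = 0.81 - b12^2 x V.

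- Common slope: b = (1' R^-1 B) / (1' R^-1 1)
- Week 12 variance, one slope: r + (b12 - b)^2 x V
- Week 12 variance, slope by visit: r x (1 + 1/280)

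**4. One case in full.** Slopes -0.1/-0.25/-0.4, V = 0.433^2 = 0.1875, higher correlations.

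- r = 0.81 - 0.16 x 0.1875 = 0.780
- b = -0.080, a fifth of the Week 12 slope
- One slope: 0.780 + 0.320^2 x 0.1875 = 0.799
- By visit: 0.780 x 1.0036 = 0.783
- Saving: 2.1%
- Share of the available variance reduction that is lost: (1 - 0.080/0.4)^2 = 64%

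**5. All cases** (ranges over baseline SD and correlation set).

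| Slopes, Weeks 2/6/12 | Common slope | Week 12 variance saved | Power at 70 per arm, one slope -> by visit |
|---|---|---|---|
| -0.3/-0.3/-0.3 | -0.30 | -0.4% | 90.7-91.0% -> 90.6-90.9% |
| -0.1/-0.2/-0.3 | -0.11 to -0.09 | 0.1-0.7% | 90.5-90.7% -> 90.6-90.9% |
| -0.1/-0.25/-0.4 | -0.11 to -0.08 | 0.6-2.1% | 90.6-90.9% -> 90.8-91.3% |
| -0.1/-0.3/-0.5 | -0.12 to -0.07 | 1.3-3.9% | 90.6-91.0% -> 91.1-91.9% |
| 0/-0.3/-0.6 | -0.03 to 0.04 | 3.3-8.9% | 90.1-90.6% -> 91.4-92.5% |
| 0/-0.4/-0.8 | -0.04 to 0.05 | 6.2-15.8% | 89.9-90.8% -> 92.2-94.2% |

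In rows 2 to 4 the common slope is 15 to 36% of the Week 12 slope, and 41 to 73% of the available variance reduction is lost. The percentages saved stay small because the narrow eligibility window limits what baseline can explain.

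**6. Simulation.** 320 subjects, 1000 runs per scenario, baseline SD 0.42, no center or prior-treatment terms, true difference -0.50. Entries are the empirical SD of the Week 12 difference, one slope v by visit.

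| Slopes | Complete data | About 9% missing at random |
|---|---|---|
| -0.3/-0.3/-0.3 | 0.1434 v 0.1435 | 0.1408 v 0.1405 |
| -0.1/-0.25/-0.4 | 0.1452 v 0.1439 | 0.1480 v 0.1457 |
| 0/-0.4/-0.8 | 0.1436 v 0.1329 | 0.1506 v 0.1394 |

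The middle row is a variance saving of 1.8% with complete data, 1 - (0.1439/0.1452)^2, and 3.1% with dropout. Mean estimates lay between -0.49 and -0.51 under both models.

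**The case against.** The best defense is that the model is prespecified, the same in protocol and SAP, and valid as it stands. Randomization protects the estimate, and the unstructured covariance absorbs the misfit into the standard error. The gain rests wholly on slopes that the documents do not give: their remarks on HbA1c kinetics say nothing about the baseline slope at each visit, and with equal slopes the extra term is a slight loss. All of this stands. It limits the point to an optional efficiency gain, but does not remove it, because the possible loss is smaller than the gain in most of the assumed range.

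A reader might infer four stronger things that the documents and the arithmetic do not support.

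- **Bias.** One might think that Week 12 values missing after rescue are projected along a wrong slope and distort the result. The simulations with dropout show essentially unbiased estimates under both models.
- **Lost power.** Protocol 9.2 uses the unadjusted SD, so its 90% at 70 per arm never relied on the covariate. Even in the extreme case, where one slope does slightly worse than no baseline term (0.1436 v 0.1423 in simulation), power is 89.9% or more.
- **Guaranteed or larger gain.** Bigger percentages arise with a smaller SD, such as 0.6, but the plan's figure is 0.9.
- **Fasting glucose, blood pressure and weight.** No calculation was made for these, and the argument from slow HbA1c accrual does not carry over to them.

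**Conclusion.** The constraint is real and nothing elsewhere in the plan relaxes it. If the baseline relation strengthens between Week 2 and Week 12, the common slope stays near the Week 2 value and most of the Week 12 slope goes unadjusted. At the plan's SD of 0.9 the gain from relaxing it is about 0.1 to 4% of the Week 12 variance in plausible scenarios, rising to about 9% with steeper divergence and about 16% in the extreme case. The downside is two parameters with three visits and about 0.3 to 0.4% of variance (1/320 to 1/280) if slopes are equal. These figures rest on the assumed slopes, early-visit SDs, correlations and baseline SD. This is a small, worthwhile precision improvement; the planned analysis is valid without it.

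**What to change.** Before unblinding:

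- Add `baseline*visit` to the MODEL statement in SAP 3.8.1 and to the sentence that lists the model terms.
- Align Protocol 9.5 and the synopsis.
- Carry the term into the analyses that reuse the model: per-protocol, multiple imputation, LOCF, post-rescue values included, and the dose-response contrasts.
- State that the term is dropped together with baseline if the treatment-by-baseline test triggers the switch to ANOVA.
- SAP 3.8.2 borrows the primary model by reference, so say whether the secondary endpoints take the term. The figures here do not settle that choice.

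The cost is one model term and matching text. The count of two parameters assumes that the analysis visits are Weeks 2, 6 and 12 only. No extra data, visits or subjects are needed.
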